## **9 STATISTICAL METHODOLOGY**

### **9.1 GENERAL METHODOLOGY**

#### Descriptive statistics

- Continuous variables will be summarized by mean, standard deviation, median, 1st quartile, 3rd quartile, minimum and maximum.
- Discrete variables will be summarized by frequencies and percentages.

All p-values will be rounded to four decimal places. Statistical significance will be declared if the two tailed p-value is less than 0.050.

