#### *11.3.6 Statistical methods*

Data from the CRFs and from the laboratory database will be converted to SAS datasets and will be analyzed using SAS® software version 9.2 for Windows®.

All p-values will be rounded to four decimal places. Statistical significance will be declared if the two tailed p-value is less than 0.05.

Descriptive statistics for continuous variables and frequency counts for categorical variables will be calculated for each variable at every assessment time point.

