#### **Secondary Efficacy Analyses**

The secondary efficacy end-points will be the change in serum levels of FT4, FT3, TT4, TT3, CPK, SHBG, ferritin, ACE level, and lipid panel at the end of each 12-week treatment period with Tirosint® capsules with respect to baseline. The change in serum levels of TSH, FT4, FT3, TT3 at Visit 3 with respect to baseline will also be analysed as secondary efficacy end-points.

Serum levels of FT4, TT4, FT3, TT3, CPK, SHBG, ferritin, ACE level, and lipid panel (TC, HDL-C, LDL-C, VLDL-C, TG) will be analyzed by means of a repeated measures analysis of covariance with basal value as covariate. The 95% confidence interval will be calculated.

Baseline variables (e.g. gender, pre-study LT4 product, LT4 dose, PPI product and dose, etc.) may also be used as covariates if appropriate.

The dose adjustment evaluated in terms of number of patients requiring changes in LT4 daily dose during the treatment period will be described using frequencies and percentages.

Changes in mean LT4 daily dose at the end of the treatment period versus baseline will be analyzed by means of a repeated measure analysis of variance model.

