#### 9.4 ANALYSIS OF EFFICACY

All efficacy variables will be analyzed in the ITT, mITT and PP populations.

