##### 9.4.2 Secondary efficacy analysis

- Serum levels of FT4, FT3, TT4, TT3, CPK, SHBG, ferritin, ACE level, and lipid panel (TC, HDL-C, LDL-C, VLDL-C, TG) at the end of each 12-week treatment period vs baseline

The secondary efficacy endpoints are the changes in serum levels of FT4, FT3, TT4, TT3, CPK, SHBG, ferritin, ACE level, and lipid panel (TC, HDL-C, LDL-C, VLDL-C, TG) at the end of each 12-week treatment period with Tirosint® capsules vs baseline.

Mixed model ANCOVA repeated measures models will be used to test differences in means of serum levels of FT4, FT3, TT4, TT3, CPK, SHBG, ferritin, ACE level, at Visit 4 vs baseline visit. As covariates will be considered the following baseline variables: Age, Sex, BMI and the prescribed Tirosint® dosage (dose/Kg). Unstructured covariance structure will be used (If a different type of covariance structure will be used details will be provided).

Normal distributions for each serum level data will be tested with Shapiro Wilks. If data results not to be distributed as a normal distribution the following methods will be applied:

- Data will be log transformed and analyzed with the ANCOVA repeated measures models described above.

- The change in serum levels of TSH, FT4, FT3, TT3 at Visit 3 vs baseline

Mixed model ANCOVA repeated measures models will be used to test differences in means of serum levels of TSH, FT4, FT3, and TT3 at Visit 3 vs baseline visit. As covariates will be considered the following baseline variables: Age, Sex, BMI and the prescribed Tirosint® dosage (dose/Kg). Unstructured covariance structure will be used (If a different type of covariance structure will be used details will be provided).

Normal distributions for each serum level data will be tested with Shapiro Wilks. If data results not to be distributed as a normal distribution the following methods will be applied:

- Data will be log transformed and analyzed with the ANCOVA repeated measures models described above.

The serum levels of TSH, FT4, FT3, TT4, TT3, CPK, SHBG, ferritin, ACE level, and lipid panel at each time point will also be summarized as continuous variables.

- LT4 dose adjustment

Frequencies and percentages of patients requiring changes in LT4 daily dose during the treatment period will be provided.

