Changes in mean LT4 daily dose/kg at the end of the treatment period versus baseline will be analyzed by a mixed model ANCOVA repeated measures model with LT4 daily dose/kg at each time point as dependent variable. Unstructured covariance structure will be used (If a different type of covariance structure will be used details will be provided).

Normal distribution for the LT4 daily dose/kg data will be tested with Shapiro Wilks.

If LT4 daily dose/kg data results not to be distributed as a normal distribution the following methods will be applied:

- Data will be log transformed and analyzed with the ANCOVA repeated measures model described above.

The secondary efficacy analysis will be performed on data with missing values replaced with LOCF method and on original data (values recorded after changes in LT4 dose will not be considered in either case).

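### One unadjusted 0.05 rule covers 13 to 18 secondary tests, so the chance of at least one false declaration of significance is far above 5%

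*SAP*

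**What the plan says.** The significance rule appears once in each document, in a general section and without reference to any endpoint. SAP 9.1: "Statistical significance will be declared if the two tailed p-value is less than 0.050". Protocol 11.3.6: "Statistical significance will be declared if the two tailed p-value is less than 0.05".

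The secondary analyses are set up as hypothesis tests. In SAP 9.4.2:

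- One set of mixed models is to "test differences in means of serum levels of FT4, FT3, TT4, TT3, CPK, SHBG, ferritin, ACE level, at Visit 4 vs baseline visit".
- A second set is used "to test differences in means of serum levels of TSH, FT4, FT3, and TT3 at Visit 3 vs baseline visit".
- For dose: "Changes in mean LT4 daily dose/kg at the end of the treatment period versus baseline will be analyzed by a mixed model ANCOVA".

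SAP 9.4.2 also lists the lipid panel among the Visit 4 endpoints, but its model sentence leaves lipids out. Protocol 11.3.6 does give them a model: the "lipid panel (TC, HDL-C, LDL-C, VLDL-C, TG) will be analyzed by means of a repeated measures analysis of covariance with basal value as covariate".

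Each endpoint is analysed several times. SAP 9.4 states: "All efficacy variables will be analyzed in the ITT, mITT and PP populations". SAP 9.4.2 then asks for every secondary analysis both with LOCF and on the original data.

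Neither document has a multiplicity adjustment, a testing order, a condition that TSH must succeed first, or an exploratory label for the secondary p-values.

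**The concern.** Followed literally, the plan turns every secondary p-value below 0.05 into a declared significant result. Each test carries its own 5% error, so across the set the chance of at least one false declaration is much larger. CPK, SHBG, ferritin, ACE and the lipids make up most of the stated secondary objective (Protocol 3.2, SAP 3.2). A single chance result among them, or among the thyroid hormones, could be reported as a significant effect of the capsule, with nothing in the plan to tell the reader how many tests stood behind it.

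**Working it through.** **Stated figures.** The documents give no family-wise error rate for the secondary tests. Their only error-rate calculation is for the primary: 48 subjects, difference 0.7, SD of differences 1.9, paired t-test, two-sided 0.05, 70% power. It reproduces: the noncentrality is 0.7/1.9 × √48 = 2.55, and the noncentral t distribution gives 70.5%. That calculation concerns TSH alone.

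**Count of secondary tests.**

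| Source | Tests | Number |
|---|---|---|
| SAP 9.4.2, Visit 4 | FT4, FT3, TT4, TT3, CPK, SHBG, ferritin, ACE | 8 |
| SAP 9.4.2, Visit 3 | TSH, FT4, FT3, TT3 | 4 |
| SAP 9.4.2, LT4 dose/kg | end of treatment vs baseline | 1 |
| Modelled in the SAP | | 13 |
| Protocol 11.3.6, lipids | TC, HDL-C, LDL-C, VLDL-C, TG | 5 |
| With lipids | | 18 |

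**Independent tests, one run per endpoint, no true change.** The chance of at least one p<0.05 is 1 − 0.95^k.

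- k = 13: 1 − 0.95^13 = 0.487
- k = 18: 1 − 0.95^18 = 0.603

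For jointly normal two-sided tests, independence is the worst case, so these are ceilings. The expected number of false declarations is 13 × 0.05 = 0.65 or 18 × 0.05 = 0.90, whatever the correlation.

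**Correlated tests.** The documents give no correlations between endpoints, so these values are assumptions. With k equally correlated normal test statistics (200,000 simulated replicates):

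| Common correlation (assumed) | 13 tests | 18 tests |
|---|---|---|
| 0.3 | 41.8% | 50.9% |
| 0.5 | 33.4% | 39.8% |
| 0.7 | 23.9% | 27.7% |

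If correlation is confined to related measures (the eight thyroid tests as one block, the five lipids as another, the remaining five independent), within-block correlations of 0.7 to 0.3 give 37% to 46% for 13 tests and 47% to 57% for 18.

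**Six runs per endpoint.** Three populations × two data versions = 6, so 13 × 6 = 78 or 18 × 6 = 108 p-values. Assume a correlation of 0.90 to 0.98 between runs of the same endpoint and 0 to 0.5 between endpoints. Reading every run at 0.05 then gives 45% to 77% (13 endpoints) or 53% to 87% (18 endpoints). If the six runs were identical, the figures would fall back to the single-run values.

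**The case against.** The best defence is context. Protocol 2.2 calls the study a pilot, and Protocol 4 calls it a preliminary evaluation. There is one primary endpoint, clearly separated from the secondaries, and the secondary objective is only to evaluate biochemical changes. Protocol 13.2 relies on an IND exemption whose criteria exclude studies meant to support a significant labelling or advertising change. Unadjusted secondary p-values are common in such studies. Intervals are also partly planned already: Protocol 11.3.6 promises 95% confidence intervals for the secondary analytes, and SAP 9.5.1 gives them for mean change in laboratory parameters in the safety summaries.

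All of this stands, and it makes the point minor. It does not remove it, because the pilot status is never carried into the significance rule.

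Three stronger readings are tempting, and the documents do not support them:

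- *A false secondary claim is more likely than not.* For the 13 tests the SAP models, the ceiling with one run each is 49%. The chance passes one half only with all 18 tests and weak or partial correlation, or when several runs are counted. Free and total hormones, the same hormones at two visits and five lipids are unlikely to be independent.
- *A chance finding is likely among the biochemical markers themselves.* For CPK, SHBG, ferritin and ACE the ceiling is 1 − 0.95^4 = 18.5%. With the five lipids it is 1 − 0.95^9 = 37.0%.
- *The lack of a control group makes the multiplicity worse.* Drift over time and regression to the mean are a separate weakness of a before-after design, and no multiplicity rule addresses them.

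**Conclusion.** The point holds as a minor one. The plan declares significance at an unadjusted 0.05 for 13 secondary tests, or 18 if the lipids are run, and the resulting family-wise error is far above 5%. With one run per endpoint it is at most 49% or 60%. At an assumed common correlation of 0.5 to 0.3 it is about 33% to 42%, or 40% to 51%. Even at 0.7 it is about 24% or 28%, roughly five times the nominal level. It is higher if all six runs are read at 0.05, and the SAP does not say which run decides a secondary endpoint.

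These figures assume that nothing truly changes and that test statistics are roughly normal. The correlations are assumed, not taken from the documents. Whether 13 or 18 applies depends on whether lipids are modelled, which the SAP leaves open. The primary TSH test is a single endpoint and is not touched by this count.

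**What to change.** In SAP 9.1 and Protocol 11.3.6, limit the significance sentence to the primary TSH analysis. In SAP 9.4.2, state that secondary endpoints are reported as estimates with 95% confidence intervals and nominal p-values labelled exploratory, with no declaration of significance. If the protocol itself is no longer to be amended, the narrowing can be recorded among the changes from the protocol that SAP 4 already lists.

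A formal correction is not proposed. The SAP gives no lipid model and no decisive run, so the set of p-values to correct is undefined. A flat split would also be costly: at 0.05/13 = 0.0038 or 0.05/18 = 0.0028, power at n = 48 for a standardised effect of 0.7/1.9 falls from 70.5% to 32.6% or 28.8%.

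The cost is wording only: no new data and no change to the primary analysis. The downside is that no secondary result can be called statistically significant, however small its p-value.

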#### Baseline definition

As baseline will be considered the last assessment before the first dose of study treatment. (i.e. date of assessment previous or equal to the start date of study treatment)

### **9.2 PATIENT DISPOSITION**

A complete screening disposition on screened patients including the number of enrolled patients, the number of screening failure, the number of patients rescreened and the reason for screening failure will be provided.

A study disposition will also be provided, it will include number of patients who completed or discontinued the study and the reason for discontinuation.

Disposition of patients who performed each visit, patients included in each analysis population and protocol deviations will be provided. To evaluate the COVID-19 impact on the study a summary of protocol deviations related to it will be provided.

### **9.3 DEMOGRAPHIC AND SCREENING/BASELINE CHARACTERISTICS**

Demographic data will include age, height, weight, BMI: those will be analyzed as summary of means. Gender and race will also be analyzed as summary of frequencies and percentages.

Patients baseline characteristics will include:

- Prior medications: those will be summarized by Anatomical Therapeutic Chemical (ATC) level 2 and Preferred Term (PT). Prior LT4/PPI treatments will be summarized separately.
- Medical and surgical history information: those will be summarized by System Organ Class (SOC) and Preferred Term (PT).
- Childbearing potential and urine pregnancy test information that will be summarized by frequencies and percentages on female patients of the following variables: childbearing potential and information about lactating, using reliable contraception, pregnancy in the next months and pregnancy test.

#### 9.4 ANALYSIS OF EFFICACY

All efficacy variables will be analyzed in the ITT, mITT and PP populations.

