Tirosint® will be taken as a single daily dose in the morning, on an empty stomach, one-half to one hour before breakfast, according to labelling. All subjects will separate their LT4 by at least 4 hours from any drug known to interfere with LT4 absorption (e.g. iron and calcium supplements, see section 6.5) and by at least 1 hour from foods that are known to interfere with LT4 absorption.

The patients will continue intake of PPI according to their individual prescription and habits.

Patients will remain on their pre-screening dose (both for LT4 and for PPI) throughout the whole study duration.

No LT4 dose adjustments will be allowed during the whole study, unless TSH levels > 10 or < 0.01 mIU/L are measured, which require immediate dose adjustment of LT4. In particular:

- If TSH levels > 10 or < 0.01 mIU/L are measured during the baseline visit the subject will drop-out, because pre- and post-switch comparisons at the same dose would not be possible.
- If TSH levels > 10 or < 0.01 mIU/L are measured during control visits (interim or unforeseen), the dose will be adjusted and the subject will remain in the study. To the purpose of the efficacy evaluation in such cases reference is made to section 11.3.

The Investigator can adjust the LT4 dose for a patient with TSH levels < 10 or ≥ 0.01 mIU/L, if this is considered necessary for the safety of a patient. The reason should be appropriately documented.

Changes in the dose of PPI are acceptable during the study provided that the dose remains ≥ 20 mg/day for omeprazole, esomeprazole and rabeprazole, ≥ 15 mg/day for lansoprazole, ≥ 30 mg/day for dexlansoprazole, and ≥ 40 mg/day for pantoprazole. If the newly prescribed dose falls outside this range or if the therapy with PPI is interrupted, the subject will drop out of the study.

Any changes will be described in the CRF.

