#### Analysis Sets

In order to assess sensitivity on efficacy analysis an additional analysis population will be defined. Modified Intention-To-Treat population will be defined as: all included patients who received at least one dose of the study medication and performed at least Visit 2 and Visit 3 laboratory assessments under the same LT4 dose with a valid TSH value.

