## **6 ANALYSIS SETS**

### **6.1 INTENTION-TO-TREAT POPULATION (ITT)/ FULL ANALYSIS SET (FAS)**

All included patients who received at least one dose of the study medication.

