### **6.4 OTHER ANALYSIS SET**

#### **MODIFIED INTENTION-TO-TREAT POPULATION (ITT)**

All included patients who received at least one dose of the study medication and performed at least Visit 2 and Visit 3 laboratory assessments under the same LT4 dose with a valid TSH value.

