#### 7.1.2 Secondary efficacy variables

The secondary efficacy variables are the serum levels of FT4, TT4, FT3, TT3, CPK, SHBG, ferritin, ACE level, and lipid panel; and the LT4 dose adjustment.

Serum levels of FT4, FT3 and TT3 will be measured at screening visit(s), at baseline, halfway through the treatment period and at the final visit. In addition, serum levels of TT4, CPK, SHBG, ferritin, ACE level, and lipid panel (TC, HDL-C, LDL-C, VLDL-C, TG) will be measured at baseline and at the end of the 12-week treatment period (Final visit).

The change in serum levels of TSH, FT4, FT3, TT3 at Visit 3 vs baseline will also be analysed as secondary efficacy endpoint.

The serum levels of TSH, FT4, TT4, FT3, TT3, CPK, SHBG, ferritin, ACE level, and lipid panel recorded after changes in LT4 dose will not be considered for the analysis.

LT4 dose adjustment will be evaluated both in terms of number of patients requiring changes in daily dose during the treatment period and as mean change in daily LT4 dose at the end of the treatment period versus baseline.

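### LT4 dose adjustment is analysed in the mITT set, which excludes patients because their dose had changed by the Visit 3 sample, so mITT cannot serve as a sensitivity check for that endpoint

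*SAP*

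**What the plan says.** SAP 7.1.2 ends its list of secondary efficacy variables with "lipid panel; and the LT4 dose adjustment". It then says how that variable is assessed: "LT4 dose adjustment will be evaluated both in terms of number of patients requiring changes in daily dose during the treatment period", and also as the mean change in daily dose from baseline. SAP 9.4.2 adds the analyses: "Frequencies and percentages of patients requiring changes in LT4 daily dose during the treatment period will be provided", plus a repeated measures model of daily dose per kg.

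SAP 9.4 assigns the analysis sets for all of this in one sentence: "All efficacy variables will be analyzed in the ITT, mITT and PP populations". Section 9.4.2 makes no exception for dose adjustment.

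The sets differ in whether they look at dose:

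- **ITT (SAP 6.1):** "All included patients who received at least one dose of the study medication". There is no dose condition.
- **PP (SAP 6.2):** ITT patients who completed without a major protocol violation. There is no dose condition.
- **mITT (SAP 6.4):** treated patients who "performed at least Visit 2 and Visit 3 laboratory assessments under the same LT4 dose with a valid TSH value".

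The mITT set is absent from the protocol. The SAP adds it under its changes from the protocol, with the reason "In order to assess sensitivity on efficacy analysis an additional analysis population will be defined".

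Protocol 6.2 covers dose changes during treatment. When TSH crosses the stated limits at an interim or unforeseen visit, "the dose will be adjusted and the subject will remain in the study". The same section lets the investigator adjust the dose for safety in other cases.

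**The concern.** For the serum variables the same-dose condition makes sense, because it isolates the change of formulation at a constant dose. For dose adjustment the condition is part of the outcome. A patient already on a different dose at the Visit 3 sample has had the event being counted, and for that reason does not enter the set in which it is counted.

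A sensitivity analysis is useful because it could disagree with the main one. On changes still in force at Visit 3, the mITT table must show zero whatever happened. A reader who sees dose adjustment reported in three sets may take agreement, or a lower mITT rate, as corroboration. One of the three could not have shown those changes. The model of mean dose per kg would also produce a p-value from the filtered sample. Change in daily LT4 dose is a stated secondary objective (Protocol 3.2, SAP 3.2), so the table is likely to be read.

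**Working it through.** **Figures in the plan.** Neither document states an expected or observed number of dose changes. The sample size section (Protocol 11.3.1, SAP 4.1) gives only a combined drop-out and dose adjustment rate of about 20%. The inflation reproduces, 48/(1 − 0.20) = 60, but the 20% is not split and says nothing about timing. SAP 4.1 reports 47 patients included and 45 completed.

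**Who is excluded because of a dose change.** Visit 3 is at day 35–49, and the study schedule shows no other TSH test between baseline and Visit 4.

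| When the change arises | On a changed dose at the Visit 3 sample? | In mITT? |
|---|---|---|
| Required by the baseline result, before any control visit | Listed reason for withdrawal (Protocol 5.4) | Outside this mechanism |
| At an unscheduled visit before the Visit 3 sample | Yes, unless returned to the original dose | No |
| Ordered on the Visit 3 result | No, the change follows the sample | Yes |
| After Visit 3 | No | Yes |

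Only the second row is lost through the outcome itself.

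**Notation.** N = ITT patients; T = patients with any dose change; E = those on a changed dose at the Visit 3 sample; M = non-changers without a valid Visit 2 or Visit 3 TSH. The remaining T − E changers are taken to have valid values.

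- ITT percentage = T/N
- mITT percentage = (T − E)/(N − E − M)

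**Count.** mITT holds at most T − E patients with a change, so the count is equal to or lower than T.

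**Percentage, with N = 47 (SAP 4.1) and M = 0.** T and E are assumptions.

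| T | E | ITT | mITT |
|---|---|---|---|
| 3 | 1 | 3/47 = 6.4% | 2/46 = 4.3% |
| 6 | 0 | 6/47 = 12.8% | 6/47 = 12.8% |
| 6 | 2 | 12.8% | 4/45 = 8.9% |
| 6 | 3 | 12.8% | 3/44 = 6.8% |
| 9 | 3 | 9/47 = 19.1% | 6/44 = 13.6% |
| 9 | 4 | 19.1% | 5/43 = 11.6% |

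**Percentage when M is not zero.** Suppose the two non-completers (47 − 45 = 2) were non-changers without a valid Visit 3 TSH.

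- T = 6, E = 0: mITT = 6/45 = 13.3%, above the ITT 12.8%.
- T = 6, E = 2: mITT = 4/(47 − 2 − 2) = 4/43 = 9.3%, so the offset is partial.

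**Mean change.** It is signed, and Protocol 6.2 allows adjustment at both high and low TSH. Assume, for arithmetic only, two early changes of −25 mcg and four later ones of +25 mcg, with M = 0.

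- ITT mean = (4 × 25 − 2 × 25)/47 = 50/47 = +1.1 mcg
- mITT mean = (4 × 25)/45 = 100/45 = +2.2 mcg

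Here mITT is the higher of the two. With the signs reversed it would be the lower, so the direction cannot be known in advance.

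**The case against.** The best defence is that a full answer is already planned. ITT is listed first and counts every change. PP has no dose condition either. The mITT set is declared as supplementary, SAP 9.2 will report how many patients fall in each set, and SAP 9.5.4 describes Tirosint dosage at each time point. The group lost is also narrow, because it needs a change at an unscheduled visit before the Visit 3 sample. All of this stands, and it limits the weight of the point. It does not make the mITT table informative for dose adjustment.

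A reader might go further in three ways that the documents do not support:

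- **That every dose change in the first half of treatment is lost.** The Visit 3 result is the main scheduled trigger for a change, and a change ordered on it comes after the sample, so that patient stays in mITT. Read literally, a patient whose dose was changed and then restored before Visit 3 could also qualify.
- **That mITT can only understate dose adjustment on every measure.** This holds for the count. The percentage can exceed the ITT figure when non-changers lack a valid Visit 3 TSH, and the mean can move either way.
- **That the selection favours the product.** The secondary objective gives no direction for the dose change. Under the primary hypothesis, that PPIs impair capsule absorption less than tablet absorption, an early dose reduction would support the product, and mITT would discard it.

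**Conclusion.** The point holds as a defect in the assignment of analysis sets. For LT4 dose adjustment, mITT membership depends on the outcome, so the mITT result cannot test the ITT result.

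The size is unknown. Under the stated assumptions for 6 changes, the rate falls from 12.8% to 8.9% or 6.8% when 2 or 3 changes are early. If no patient was on a changed dose at the Visit 3 sample, this mechanism has no effect. The illustration rests on 47 treated patients, assumed values of T and E, and valid Visit 2 and Visit 3 TSH in everyone else.

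The primary endpoint, the serum variables, the sample size and the ITT and PP dose results are not affected by this selection. The change should be made because it is nearly free and removes a table that could be misread.

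**What to change.** In SAP 9.4, replace the single sentence on analysis sets with wording such as:

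> Serum-level efficacy variables will be analysed in the ITT, mITT and PP populations. LT4 dose adjustment (number of patients and mean change) will be analysed in the ITT and PP populations only, because mITT membership depends on the LT4 dose being unchanged at Visit 3.

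PP must stay: Protocol 11.3.2 requires all efficacy variables in both ITT and PP, so restricting dose adjustment to ITT alone would create a new departure from the protocol.

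The cost is one sentence and fewer tables, with no new data. If the mITT dose tables already exist, the minimum is a footnote saying that membership requires the same LT4 dose at Visits 2 and 3.

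A neighbouring line should be clarified in the same edit. The last paragraph of SAP 9.4.2 sets aside values recorded after a dose change for the whole secondary analysis, whereas SAP 7.1.2 and 8 limit that rule to laboratory values. The SAP should say that it does not apply to the dose itself.
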